#### 9.2.2. Pharmacokinetic Criteria for Stopping Doses

There are no pharmacokinetic criteria for stopping study drug doses.

### 9.3. Treatment Compliance

At each scheduled study visit after randomization, the Investigator or designee will interview the patient regarding treatment compliance and compare the number of dispensed versus returned study drug tablets. Patients should strive for 100% compliance with the daily dosing schedule. Retraining on treatment compliance should occur for patients with less than 80% compliance at any visit and the Sponsor should be notified.

### 9.4. Study Drug Materials and Management

Please consult the Pharmacy Manual for a complete description of the study drug and requirements for storage, handling, dispensing, accountability, returns and destruction.

#### 9.4.1. Physical Description of Study Drug

Study drug will include CTP-543, a deuterated analog of ruxolitinib, and matching placebo. Details regarding formulation and dosage are presented in [Table 4](#).

**Table 4: Investigational Product**

	Investigational Product (CTP-543 or Placebo)
Product Name:	CTP-543 or Matching placebo
Dosage Form:	Tablet
Dosage Strength of CTP-543	4 mg, 8 mg, 12 mg
Route of Administration	Oral
Physical Description	White, capsule-shaped tablets

#### 9.4.2. Study Drug Packaging, Labeling, and Storage

CTP-543 active and placebo tablets will be packaged and labeled by an appropriately qualified vendor. Each patient will receive a dosing card at each 4 week study visit. Details of the packaging, labeling and dispensing instructions can be found in the Pharmacy Manual.

The label(s) for the investigational product and placebo will include sponsor name, address and telephone number, the protocol number, investigational product name, dosage form, amount of investigational product per container, lot number, unique dosing card number, storage conditions, and required caution statements and/or regulatory statements, as applicable. Additional information may be included on the label as applicable per local regulations.

Adequate supplies of study drug will be provided to each site. Study drug should be stored in the original package between 15°C to 25°C (59°F to 77°F), as stated on the product label, in a secure, temperature-monitored, locked area, under the responsibility of the Investigator or other authorized individual until dispensed to the patients.

Study drug dispensed to patients should be stored in the original package at room temperature as stated on the package label. No special handling procedures are required.

#### **9.4.3. Study Drug Preparation and Administration**

No study drug preparation is required. Patients will take the first dose of study drug in the clinic on Day 1 and will be instructed to take study drug every 12 hours for the duration of the Treatment Period. Patients should dose study drug in the clinic on all Study Visit Days after clinical laboratory blood draws are completed.

Study drug should be taken at approximately the same times each day, with water, and with or without meals. Patients should be instructed to take study drug as prescribed according to the Week, Day, and Time of day designations in the dosing card. If a dose is missed, the patient should skip the missed dose and resume dosing at the next scheduled dose. The patient should not take two doses at the same time. Deviations from prescribed dosing should be discussed at each visit for assessment of compliance and retraining when necessary.

#### **9.4.4. Study Drug Return and Disposal**

The Sponsor (or designee) will review with the Investigator and relevant site personnel the process for study treatment return, disposal, and/or destruction, including responsibilities for the site versus the Sponsor (or designee). Specific requirements for destruction or return are defined in the Pharmacy Manual.

#### **9.4.5. Study Drug Accountability**

To satisfy regulatory requirements regarding drug accountability, all study drug will be reconciled in full. The Investigator or designee must maintain accurate records of the receipt of study drug, including date received, lot number, amount received, condition of the package, and the disposition of study drug.

Current dispensing records will also be maintained, including the date and amount of medication dispensed to each individual patient. Returned study drug records will be maintained and final study drug reconciliation will also be recorded for each patient.

### **9.5. Concomitant Medications and Procedures**

All medications, including over-the-counter therapies (e.g., vitamins, herbal, and nutritional supplements), taken at the time of the Screening Visit through the Follow-Up Visit will be recorded in the patient's source documentation and documented in the eCRF.

If taking thyroid medication, the patient must maintain thyroid stimulation hormone levels within the normal range for 6 months prior to Screening and throughout the study.

Any concomitant medication deemed necessary for the wellbeing of the subject may be given at the discretion of the Investigator. Use of medications that are prohibited per protocol will require patient withdrawal from the study.

The following treatments are not permitted during the study:

- Medications that may affect hair regrowth or immune response (such as: corticosteroids administered orally, by injection, or applied to areas of skin affected by alopecia; platelet-rich injections; topical application to affected areas of anthralin, squaric acid, diphenylcyclopropenone, or minoxidil;
- Treatment with systemic immunosuppressive medications including but not limited to methotrexate, cyclosporine, and azathioprine; chloroquine derivatives; Janus kinase inhibitors (ruxolitinib, tofacitinib, etc), etanercept; or biologics (adalimumab, atlizumab, canakinumab, certolizumab, fontolizumab, golimumab, infliximab, mepolizumab, rituximab, secukinumab, tocilizumab, ustekinumab);
- Use of strong CYP3A4 inhibitors (such as, but not limited to clarithromycin, conivaptan, grapefruit juice, indinavir, itraconazole, ketoconazole, lopinavir/ritonavir, mibefradil, nefazodone, nelfinavir, posaconazole, saquinavir, telaprevir, telithromycin, voriconazole, or fluconazole) dosed for systemic exposure;
- Use of strong CYP3A4 inducers (such as, but not limited to barbiturates, carbamazepine, efavirenz, glucocorticoids, modafinil, nevirapine, oxcarbazepine, phenobarbital, phenytoin, pioglitazone, rifabutin, rifampin, St. John's Wort, or troglitazone) dosed for systemic exposure.

## 10. STUDY ASSESSMENTS AND PROCEDURES

The schedule of assessments and procedures is presented in [Table 1](#) and should be referenced for details regarding the collection of each assessment at each visit in the respective cohort periods.

### 10.1. Demographic Characteristics and Medical History

Demographic characteristics (i.e., sex, ethnic origin, date of birth, and calculated body mass index) will be collected at the Screening Visit, between Day -28 and -1, and detailed on the eCRF.

The patient's alopecia areata will be classified by the Investigator into one of three categories defined for this study:

- 1) Alopecia areata: patchy type hair loss,
- 2) Alopecia totalis or universalis: complete hair loss on the scalp with or without body hair loss,
- 3) Alopecia ophiasis: band-like hair loss limited to the periphery of the scalp along the back of the hair line in the occipital region and possibly extending over each ear in temporal regions.

Key criteria that distinguish alopecia areata from other forms of hair loss may include abrupt onset of disease, a history of recurrence and spontaneous remission, response to topical or intralesional steroid treatment, and distribution of hair loss pattern. Care must be taken during the evaluation to assess for other causes of hair loss such as trichotillomania, or scarring alopecia and other forms of non-scarring alopecia. Evidence of thinning hair should be distinguished from pattern hair loss or telogen effluvium and evidence of inflammation should be investigated to rule out infection, as appropriate.

Thorough medical history, including current medications, nail and facial hair involvement, comorbidities, serious infection history and exposure risk, including HIV, as well as history or vaccination against herpes zoster will be collected at the Screening Visit, and at the Randomization Visit on Day 1 for each cohort.

Medical history should be thoroughly probed for potential exposure to serious infections such as HIV, history or vaccination against herpes zoster or other recent live virus vaccinations, as well as cancer risk due to the potential immunosuppressive properties of CTP-543 and known adverse events associated with JAK inhibitors.

### 10.2. Severity of Alopecia Tool (SALT)

The SALT score was introduced as part of investigative guidelines published by the National Alopecia Areata Foundation [[Olsen, 2004](#)]. The SALT is a measure of hair absence that quantifies the amount of scalp surface without hair in a pre-specified quadrant of the scalp (right side, top, left side, back), that is further summed after applying a quadrant-specific multiplier indicative of scalp surface area contribution, to provide an overall score of total hair loss. The SALT assessment will occur via live examination of the patient during clinic visits.

SALT will be used to determine efficacy for the study. To reduce variability, one rater should perform the SALT assessment for the patient for the duration of the study. All investigators using the SALT should be trained prior to use. Please consult the associated Site Operations Manual

for additional details regarding SALT scoring and training requirements for this study. An example of the SALT assessment tool is provided in [Appendix 17.1](#).

### **10.3. Photographs**

Photographs will be taken of each patient's scalp to provide visual support of Baseline assessment of SALT as well as potential changes in SALT scores throughout the study. No formal analyses of photographs will occur. Scalp photographs will correspond to the 4 defined quadrants of the SALT assessment and will be taken when SALT assessments are performed.

For those patients with eye and nail involvement in their alopecia areata phenotype, a photograph of the eyes and hands for eyelash/eyebrow and nail involvement, respectively, will be taken to document potential changes throughout the study compared to Baseline. No formal analyses of photographs will occur.

### **10.4. Global Impression Scales**

The Global Impression Scales are measures commonly used in clinical trials to allow integration of several sources of information into a single rating of the patient's condition. The Global Impression Scales employ a 7-point Likert scale measuring either disease state severity or improvement after treatment. The alopecia areata assessments should consider the condition of the patient at the time of the assessment compared to Baseline.

In this study, the Global Impression Scale of Improvement will be performed by both the clinician and the patient at selected times during the study as indicated in [Table 1](#).

#### **10.4.1. Clinical Global Impression of Improvement (CGI-I)**

Compared to the patient's alopecia areata prior to treatment at Baseline, the patient's current state of alopecia areata will be assessed according to the Investigator's perceived change. The Investigator may select one of seven numeric choices representing "Very Much Worse" to "Very Much Improved". To reduce variability, one rater should perform the CGI-I assessment for the patient for the duration of the study. An example of the CGI-I is provided in [Appendix 17.2.1](#).

#### **10.4.2. Patient Global Impression of Improvement (PGI-I)**

Compared to the patient's alopecia areata prior to treatment at Baseline, the patient's current state of alopecia areata will be assessed according to his/her perceived change. The patient may select one of seven numeric choices representing "Very Much Worse" to "Very Much Improved". An example of the PGI-I is provided in [Appendix 17.2.2](#).

### **10.5. Patient Reported Outcomes: Alopecia Areata Symptom Impact Scale (AASIS) and Exploratory Questions**

The AASIS is a questionnaire designed to measure the quality of life, symptoms, and their impact for patients with alopecia areata [[Mendoza, 2013](#)]. Three dimensions related to alopecia areata are assessed: impact of alopecia areata, hair loss, and physical skin symptoms. An example of the AASIS is provided in [Appendix 17.3.1](#).

In addition to the AASIS, exploratory questions will be used to attempt to define clinically meaningful outcomes for patients with alopecia areata. The exploratory questions are provided in [Appendix Section 17.3.2](#).

## 10.6. Visual Analog Scale (VAS)

The visual analog scale is a scale of continuous measure initially developed for pain that has been used in a variety of clinical settings where the endpoint of interest is based on a subjective perception. The visual analog scale is a distinct 100 millimeter line anchored on the left end at full degree of impairment and on the right end at no degree of impairment, where indication of the degree of impairment perceived at the time of assessment is captured by marking the appropriate position on the line between the anchor points. The measured distance of the mark from the left anchor will be recorded in millimeters.

### 10.6.1. Clinician VAS of Severity (VAS-S)

The Investigator will complete a VAS-S regarding the severity of the patient's alopecia areata at the time of completion as indicated in the Schedule of Events. The left and right anchor points for the clinician VAS-S are "Extremely Apparent" and "Not At All Apparent", respectively. To reduce variability, one rater should perform the VAS-S assessment for the patient for the duration of the study. An example of the clinician VAS-S is provided in [Appendix 17.4.1](#).

### 10.6.2. Patient VAS of Severity (VAS-S)

As specified in the Schedule of Events, patients will rate perception of his/her alopecia areata severity on the patient VAS-S. The left and right anchor points for the patient's alopecia areata VAS-S are "Extremely Apparent" and "Not At All Apparent", respectively. The patient VAS-S will measure the patient's perception of his/her alopecia areata at the time of completion. An example of the patient VAS-S is provided in [Appendix 17.4.2](#).

## 10.7. Pharmacokinetic Assessments

Whole blood (4 mL each) will be collected in K2EDTA vacutainer collection tubes at the following time points to evaluate plasma concentrations of CTP-543 and metabolites.

- Day 1 and Week 4: 2 samples at each visit; 1 sample pre-dose, and 1 sample post-dose at the end of the visit
- Week 2: 1 sample pre-dose with the safety lab draw
- Weeks 8, 24: 1 sample post-dose at the end of the visit

The exact time of blood collection as well as the exact time of the preceding dose will be recorded. The Week 4 pre-dose draw is the time point intended to examine steady-state trough levels of study drug, and therefore the preceding dose will not be observed in the clinic. To document the preceding dose time, patients should be instructed to record the last dosing time prior to the Week 4 Visit in their dosing card. All attempts to adhere to the pharmacokinetic schedule should be made. However, the inability to follow the schedule or to obtain/process a sample will not be considered a protocol deviation.

Instructions for harvesting and preparing plasma samples prior to freezing and additional procedures for blood sample collection will be provided in separate study laboratory manual.

## 10.8. Vital Signs, Weight, and Height

Vital signs will be measured after the patient has been in a supine or semi-supine position for at least 5 minutes and will include blood pressure, pulse rate, respiratory rate, and oral temperature.

Weight will be measured per institution standard of care. Patients should wear light clothing and remove his/her shoes before weight is measured. Height will be measured per institution standard of care, after the patient has removed his/her shoes. Height will only be measured at the Screening Visit. Weight and vital signs will be measured at each study visit according to the Schedule of Events. Weight and height will be used to calculate the patient's body mass index at Screening. Weight and height will be converted as needed to kilograms and centimeters, respectively, prior to statistical analyses.

### **10.9. Physical Examination**

A complete physical examination will include an examination of all major organ systems, with an emphasis on assessing for active signs and symptoms of infection including tuberculosis, and will be performed as indicated in the Schedule of Events. Brief physical examinations including abdominal palpation, and head, eyes, ears, nose and throat assessment in addition to assessing for active signs and symptoms of infection, including tuberculosis, will be performed at all other intermediate visits as specified in [Table 1](#). Patients should be instructed to notify the clinic of any signs of infection between visits for appropriate monitoring and follow-up.

### **10.10. Electrocardiogram**

Twelve-lead electrocardiograms will be performed after the patient has rested in a supine or semi-supine position for at least 5 minutes. Individual parameters including heart rate, PR, QT, QTcF, QRS, and RR intervals will be collected. Repeat electrocardiograms (if deemed necessary) should be performed at least 5 minutes apart. The Investigator should indicate review of the electrocardiogram reports throughout the study by signing and dating each report.

### **10.11. Clinical Laboratory Assessments**

Clinical laboratory assessments are presented in [Table 5](#). Clinical laboratory samples should be collected at the beginning of each clinic visit and just prior to a dose on all Study Visit Days.

The results of clinical laboratory tests conducted at the Screening Visit (and prior to dosing) must be assessed by the Investigator to determine each patient's eligibility for participation in the study. The Investigator should indicate review of the laboratory reports throughout the study by signing and dating each report.

All clinical laboratory results that fall outside the reference range will be interpreted by the Investigator as Abnormal, not clinically significant, or Abnormal, clinically significant. Laboratory results deemed Abnormal, clinically significant will be recorded as an adverse event in the eCRF and should be fully investigated and repeated for verification. Clinically significant laboratory abnormalities indicative of hematologic or other effects requiring intervention should be discussed with the Medical Monitor. Additional tests and evaluations required to establish the significance or etiology of a clinically significant abnormal result or to monitor the course of an adverse event should be obtained when clinically indicated. Whenever possible, the etiology of the clinically significant abnormal findings will be documented on the eCRF.

Any significant laboratory abnormalities that are either serious or unexpected will be promptly reported to the Sponsor. Any additional relevant laboratory results obtained by the Investigator during the course of this study will be reported to the Sponsor or designee.

**Table 5: Clinical Laboratory Assessments**

Hematology	Chemistry	Serum Pregnancy
Complete blood count Absolute neutrophil count Absolute eosinophil count Platelet count White blood cell count with differential Absolute reticulocyte count Hemoglobin A1c	Alanine aminotransaminase Albumin Alkaline phosphatase Amylase Aspartate aminotransaminase Total bilirubin Direct bilirubin Indirect bilirubin Blood urea nitrogen Calcium Carbon dioxide Chloride Creatinine Creatine kinase Glucose Lipase Total protein Phosphorus Potassium Sodium Uric Acid	Human chorionic gonadotropin (females of childbearing potential only)
Serology	Lipids	Other
Hepatitis B virus Hepatitis C virus	Total cholesterol Low-density lipoprotein High-density lipoprotein Triglycerides	Tuberculosis Thyroid stimulating hormone

### 10.12. Pharmacodynamic Assessments

Blood samples will be collected for potential future exploration of the pharmacodynamic properties associated with CTP-543 dosing. Two milliliters of whole blood will be collected into a PAXgene® Blood RNA tube and 4 milliliters of whole blood will be collected in a K2EDTA vacutainer collection tube. Pharmacodynamic samples will be collected at the following time points:

- Day 1: pre-dose
- Week 2: pre-dose with the safety lab draw
- Weeks 4, 8, 24: post-dose at the end of the visit

Collection of samples should be in conjunction with safety or pharmacokinetic blood draws when possible. All attempts to adhere to the pharmacodynamic schedule should be made. However, the inability to follow the schedule or to obtain/process a sample will not be considered a protocol deviation.

Instructions for harvesting and preparing samples prior to storing or freezing, and additional procedures for blood sample collection will be provided in a separate study laboratory manual.

Information obtained from these potential analyses would be limited to JAK-signaling related investigations only and would not be used for diagnostic purposes, generation of cell lines, or commercial uses, nor would results of individual patients be disclosed. However, results of the

blinded pharmacodynamic studies data may be presented or published in scientific or medical settings.

### **10.13.    **Unscheduled Visit****

In addition to regularly scheduled protocol visits, an Unscheduled Visit may be conducted to ensure appropriate safety monitoring or follow-up of the patient, at the discretion of the Investigator. For example, an Unscheduled Visit may be scheduled to monitor potential or actual clinically meaningful safety laboratory results, for confirming hematology results to support dose interruption or resumption of dosing thereafter, for suspicion of tuberculosis, or for other clinical signs, symptoms, or considerations that warrant additional safety follow-up. Only those criteria requiring additional monitoring should be performed at an Unscheduled Visit. An Unscheduled Visit will not replace regularly scheduled protocol visits.

## **11. ADVERSE EVENTS**

### **11.1.1. Definition of Adverse Event**

An adverse event is any untoward medical occurrence that may appear or worsen in a patient during the course of a study. It may be a new intercurrent illness, a worsening concomitant illness, an injury, or any concomitant impairment of the patient's health, including laboratory test values, regardless of etiology. Any worsening (ie, any clinically significant adverse change in the frequency or intensity of a pre-existing condition) should be considered an adverse event. A diagnosis or syndrome should be recorded on the adverse event page of the eCRF rather than the individual signs or symptoms of the diagnosis or syndrome. A worsening of the condition under study, alopecia areata, will not be reported as an adverse event.

All patients will be monitored for adverse events during the study. Assessments may include monitoring of the following parameters: the patient's clinical symptoms, laboratory, physical examination findings, or findings from other tests and/or procedures.

An adverse event reported after informed consent, but before the first dose of study drug (ie, Day 1), will be considered a pretreatment adverse event and will be captured on the eCRF. Adverse events will be considered treatment-emergent if the onset is after the first dose of study drug.

An abnormal laboratory value is considered to be an adverse event if the abnormality:

- results in discontinuation from the study;
- is judged by the Investigator to be of significant clinical importance requiring treatment, modification/interruption of investigational product dose, or any other therapeutic intervention

Regardless of severity grade, only laboratory abnormalities that fulfill a seriousness criterion need to be documented as a serious adverse event.

If a laboratory abnormality is one component of a diagnosis or syndrome, then only the diagnosis or syndrome should be recorded on the adverse event eCRF. If the abnormality was not a part of a diagnosis or syndrome, then the laboratory abnormality should be recorded as the adverse event. If possible, the laboratory abnormality should be recorded as a medical term and not simply as an abnormal laboratory result (e.g., record thrombocytopenia rather than decreased platelets).

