#### **12.4.6. Safety**

All safety summaries will be descriptive with no statistical hypothesis testing and based on the Safety Population. Patients will be summarized according to the study drug received (i.e., as treated), should it differ from the randomized treatment arm. All safety endpoints will be listed in by-patient data listings.

Adverse events will be coded using MedDRA and summarized by system organ class and preferred term. Clinically significant deteriorations in physical examination findings will be reported and summarized as adverse events.

Laboratory values will be converted to the project-defined unit of measurement, as applicable, before analysis. Abnormal, clinically significant laboratory values will be reported and summarized as adverse events.

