### **Clinical Laboratory**

Clinical laboratory variables will be presented in 3 ways. First, change from Baseline to each scheduled assessment will be summarized descriptively. Baseline will be defined as the laboratory value obtained before the first dose of study drug on Day 1; if Day 1 values are unavailable, then values obtained at the Screening Visit will be used.

Second, treatment-emergent potentially clinically significant (PCS) laboratory values will be identified. Potentially clinically significant values are defined as those that meet Grade 3 or Grade 4 toxicity criteria from the CTCAE criteria. Treatment-emergent PCS laboratory values are those in which the baseline value is not PCS and the post-baseline value is PCS. The number and percentage of patients with treatment-emergent PCS laboratory values will be summarized by treatment group for each clinical laboratory variable.

Third, the number and percentage of patients with Abnormal, clinically significant laboratory values (per Investigator judgment) will be summarized by treatment group for each clinical laboratory variable.

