9.3 Clinical Laboratory Evaluation

Observed measurements along with change from baseline for each scheduled assessment will be summarized descriptively by treatment group and visit for each clinical laboratory parameter.

Hematology parameters for patients that meet Grade 3 or Grade 4 toxicity criteria from the CTCAE v4.0 for neutrophils, platelets, and hemoglobin will be summarized for each scheduled visit and overall for all post-baseline visits. In addition, hematology parameters of interest that meet Grade 3 or Grade 4 toxicity criteria will be plotted as mean values over time. Serum chemistry parameters for patients that meet Grade 3 or Grade 4 toxicity criteria from the CTCAE v4.0 for total cholesterol, low-density lipoprotein (LDL) cholesterol, high-density lipoprotein (HDL), and triglycerides will be summarized for each scheduled visit and overall for all post-baseline visits.

Laboratory values will be converted to the project-defined unit of measurement, as applicable, before analysis. If laboratory values are recorded as above or below a threshold (i.e. “<2”, “>30”,

etc.), they will be counted as missing for continuous summaries. Abnormal, clinically significant laboratory values (per Investigator judgment) will be reported and summarized as AEs.

All laboratory parameter results will be included in by-patient data listings. Reference ranges for each clinical laboratory parameter will also be summarized in a data listing.

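### Two laboratory-to-AE rules are left unreconciled, and the SAP drops one and narrows another of the protocol's patient counts that do not depend on AE recording, declaring neither change

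*Protocol*

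**What the plan says.** **Recording.** Protocol 10.11 asks the investigator to rate each out-of-range result and then states: "Laboratory results deemed Abnormal, clinically significant will be recorded as an adverse event in the eCRF". The analysis sections build on that rule. Protocol 12.4.6 says "Abnormal, clinically significant laboratory values will be reported and summarized as adverse events", and SAP 9.3 says "Abnormal, clinically significant laboratory values (per Investigator judgment) will be reported and summarized as AEs".

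Protocol 11.1.1, the section that defines an adverse event, gives two conditions under which an abnormal value is one: it "results in discontinuation from the study", or it "is judged by the Investigator to be of significant clinical importance requiring treatment, modification/interruption of investigational product dose, or any other therapeutic intervention".

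**Displays.** The Clinical Laboratory part of Protocol 12.4.6 plans three:

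1. "First, change from Baseline to each scheduled assessment will be summarized descriptively".
2. Treatment-emergent potentially clinically significant (PCS) values, meaning CTCAE Grade 3 or 4 after a baseline that was not PCS: "The number and percentage of patients with treatment-emergent PCS laboratory values will be summarized by treatment group for each clinical laboratory variable".
3. For each laboratory variable, "the number and percentage of patients with Abnormal, clinically significant laboratory values (per Investigator judgment) will be summarized by treatment group".

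SAP 9.3 keeps the first. It describes Grade 3-4 summaries for neutrophils, platelets, hemoglobin, total cholesterol, LDL, HDL and triglycerides. It has no counterpart to the third, and none appears in the table list in SAP Section 14. SAP Section 1 undertakes to document departures from the protocol's analyses. Section 12, which lists them, mentions no laboratory display.

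**The concern.** The two recording rules cover different sets of results. A value rated clinically significant that is only repeated and watched is an event under 10.11 but satisfies neither condition in 11.1.1. Section 10.11 itself separates the two sets: it singles out, for discussion with the Medical Monitor, the significant abnormalities that need intervention. Sites can follow different sections in good faith, and the laboratory AE tables will then mix two practices.

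The protocol's third display would have limited the damage. It rests on the investigator's rating, whether or not an AE was entered. Once it is dropped, the SAP has no patient-level count of investigator-judged significant values that is independent of AE recording.

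This matters because cytopenias and lipid elevations are among the risks that Protocol 4.4.1 takes from the parent compound's label, and because Protocol 8.5 lists a trend in moderate or severe events within an organ system as a possible trigger for an unscheduled DMC review. Milder abnormalities that are only monitored are where the two rules part.

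**Working it through.** The documents state no figure to reproduce, so the check is a comparison of texts.

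**Step 1: which results are affected.** Each case assumes that the investigator rates the value clinically significant.

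| Case | 10.11 | 11.1.1 | SAP count taken from laboratory values |
|---|---|---|---|
| Neutrophils below the Protocol Table 3 limit | AE | Met, through dose interruption | Yes, Grade 3-4 |
| Neutrophils between 1.0 and 1.5 x 10^9/L, only monitored | AE | Not met | None |
| Lipid rise below Grade 3, untreated | AE | Not met | None |
| Liver enzyme, creatine kinase or lipase at Grade 3-4, only monitored | AE | Not met | None |

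Table 3 labels neutrophils of 0.5 to 1 as Grade 3 and sets recovery above 1.5, so the second row lies between those two limits. Table 3 has no lipid entry. In the last three rows the value survives outside the AE tables only in visit-level summaries and listings. SAP 9.3 also treats results reported as above or below a threshold as missing in the continuous summaries.

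**Step 2: what the SAP keeps.**

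| Protocol display | Depends on AE recording? | SAP |
|---|---|---|
| 1. Change from baseline, all variables | No | Kept (Tables 14.3.4.1.1 and 14.3.4.1.2) |
| 2. Treatment-emergent Grade 3-4, all variables | No | Narrowed to 3 + 4 = 7 parameters; baseline condition not restated (Tables 14.3.4.2.1 and 14.3.4.2.2) |
| 3. Investigator-rated significant, all variables | No; depends on the rating | No table |

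Of three planned displays, one is kept in full, one is narrowed and one is dropped. Protocol Table 5 lists 21 analytes under chemistry, apart from the four lipids. None of the 21 is in the Grade 3-4 laboratory-value summary that SAP 9.3 describes.

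The missing baseline condition matters little for cytopenias, because the Screening exclusions already remove low counts. It matters more for lipids: they are first measured on Day 1 and no eligibility limit applies to them.

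**Step 3: scale, on assumed rates.** Take an arm of 150/4 = 37.5, about 38 patients. Let q be the share with a significant laboratory value (assumed 5% to 20%) and a the share of those needing action (assumed 25% to 100%).

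- Rule in 10.11: 38 x q = 1.9 to 7.6 patients with an event.
- Rule in 11.1.1: 38 x q x a = 0.5 to 7.6 patients.
- Gap: 38 x q x (1 - a), from 0 to 38 x 0.20 x 0.75 = 5.7 patients.

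These figures only return the assumptions, and they set every site on one rule against every site on the other. Mixed practice would give a smaller gap.

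**The case against.** The best defence is that 11.1.1 says if, not only if. Its general definition of an adverse event already includes laboratory values, so the two conditions can be read as sufficient and 10.11 as the operative instruction. A site that obeys every section then records under 10.11, and the third display would largely repeat the AE tables. This reading is available, but nothing in 11.1.1 points the reader to 10.11. The duplication is also incomplete: 11.1.1 folds a value into a diagnosis when it is part of one, so AE terms are not counts by variable.

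Three stronger readings are tempting, and the documents do not support them.

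- *The SAP removes the only laboratory display that is independent of the AE rules.* It does not. Change from baseline remains for every parameter, and Grade 3-4 summaries from laboratory values remain for the three hematology and four lipid parameters.
- *Recording drifts between cohorts and so biases the dose comparison.* Dose is tied to cohort and placebo is pooled, so such drift would matter. But nothing shows that it occurred: the amendment history records no change to the AE definition, and within each cohort active and placebo are randomized and blinded.
- *The counts can never be rebuilt.* All results are listed. Whether the listings carry the investigator's rating is unknown, because the shells are a separate attachment.

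It is also fair that cytopenias below the Table 3 limits meet both rules, and that safety summaries are descriptive with no testing.

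**Conclusion.** The point holds within limits. The two recording rules are not reconciled. The SAP drops the third laboratory display and narrows the second from every variable to seven parameters, and SAP Section 12 declares neither change. SAP Table 14.3.5.3 keeps a table of clinically significant abnormalities for the electrocardiogram, so the laboratory omission may be an oversight, though that is inference.

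The gap has two parts: investigator-judged significant values below Grade 3 that needed no intervention, and Grade 3-4 values of other chemistry, which are counted only if someone entered an AE. How many patients this concerns cannot be derived from the documents. The conclusion assumes that some sites work from 11.1.1 alone, which is plausible but not shown. The undeclared changes to the displays stand whether or not that is so.

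**What to change.** 1. In SAP 9.3 and the Section 14 table list, restore the protocol's third display: patients with investigator-rated significant values, by treatment group and laboratory variable, for all three cohorts, built from the rating that 10.11 already requires.
2. Restore the treatment-emergent Grade 3-4 table for all laboratory variables, with the baseline condition stated.
3. List any departure that remains in SAP Section 12.
4. Reconcile Protocol 10.11 and 11.1.1 into one recording rule. Protocol 12.4.6 and SAP 9.3 already assume the 10.11 rule, so aligning 11.1.1 with it needs the fewest edits.
5. Before database lock, check results flagged clinically significant against AE records in every cohort. SAP Section 11 shows that Cohorts 1 and 2 had Week 24 data and no further enrollment by the interim analysis, so new wording alone would reach mainly Cohort 3 and could itself create a difference in recording tied to dose.

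The cost is a few extra tables, some data queries, and possibly slightly higher laboratory AE counts. Item 1 assumes that the rating is in the database. If it stands only on signed laboratory reports, it must first be entered.
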